4 STUDY DESIGN AND DOSE RATIONALE

4.1 Overall Study Design

The study is an open-label, dose-finding study to determine the optimal dose for LN visualization, as part of lymphatic mapping, in adult participants with breast cancer and melanoma undergoing SLN biopsy as part of Standard of Care (SoC).

Enrollment of breast cancer and melanoma participants will be performed independently and simultaneously. Dose level 2 (0.2 mg) will enroll the first 3 participants in each indication and then the Visualization Review Committee (VRC) will review the data for the breast cancer group and the melanoma group separately. If LN visualization with histopathologic confirmation occurs in the first 3 participants in each indication, then dose level expansion will occur and an additional 3 participants in each indication will be enrolled first with the 0.05 mg dose, followed by another 3 participants with the 0.6 mg dose. An interim analysis will be performed across initial dose levels (0.05, 0.2 and 0.6 mg) separately for breast cancer and melanoma by the VRC prior to further enrollment of participants.

If < 3 participants at 0.2 mg dose level have LN visualization with histopathologic confirmation on VRC review, 3 participants will be enrolled sequentially in the 0.6 mg and 1 mg dose levels. An interim analysis will then be performed across initial dose levels (0.2, 0.6 and 1 mg) separately for breast cancer and melanoma by the VRC prior to further enrollment of participants.

Dose Arm/IP Name	ASP5354 Dose Level	ASP5354 Dose Conc and Volume	Number of Participants
Breast Cancer and Melanoma 0.05 mg/ASP5354	0.05 mg	1.0 mg/mL, 0.05 mL in total	Up to 12
Breast Cancer and Melanoma 0.2 mg/ASP5354	0.2 mg	1.0 mg/mL, 0.2mL in total	Up to 12
Breast Cancer and Melanoma 0.6 mg/ASP5354	0.6 mg	1.0 mg/mL, 0.6 mL in total	Up to 12
Breast Cancer and Melanoma 1 mg/ASP5354	1 mg	1.0 mg/mL, 1 mL in total	Up to 12
Breast Cancer and Melanoma 2 mg/ASP5354	2 mg	1.0 mg/mL, 2 mL in total	Up to 12
Breast Cancer 4 mg/ASP5354	4 mg*	1.0 mg/mL, 4 mL in total	Up to 12

Conc: concentration

* The 4 mg dose level will be added only for breast cancer participants.

Depending on the outcome of the interim VRC analysis, additional participants may be added to the same dose level, a dose level may be closed, or a new dose level (1 mg, 2 mg or 4 mg [breast cancer only]) will begin enrollment. Up to 12 participants will be assigned at each dose level for both breast cancer and melanoma.

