Participants will receive Tc-99mSC or Lymphoseek as part of SoC for SLN biopsy. In case the participant needs other surgery (e.g., lumpectomy, mastectomy etc.) on the same day of study drug administration, the other surgery is allowed once the SLN biopsy has completed. In the operating room, participants will receive ASP5354. After administration of ASP5354, visualization of the LN(s) will be assessed using a NIR-F imaging system followed by confirmation with the gamma probe. Once lymphatic mapping is completed, gamma probe will be used per SoC. For all the LNs observed by ASP5354, gamma probe will be attempted to measure radioactivity. If the LN is not observed with NIR-F after approximately 15 minutes following injection for breast cancer participants and approximately 15 to 30 minutes for melanoma participants depending on the location of the tumor and LNs, the investigator can proceed to use the gamma probe for LN detection. When the LN is detected with the gamma probe first, radioactivity will be measured and then NIR-F imaging should be attempted again for LN visualization. For participants with melanoma, usage of lymphoscintigraphy or SPECT as part of SoC is also allowed.

The visualization data to be collected will consist of the following:

- The visualization of the LN(s) will be assessed by the investigator intraoperatively using a binary “Yes or No” question.
 - If “Yes,” the time of surgical identification of LN(s) will be collected by the investigator.
 - If “Yes,” the number of LNs visualized and the number of LNs visualized with histopathology confirmed LN will be also assessed by the investigator.
Note: Histopathology review will be conducted per standard practice at each site.
- Transdermal visualization of lymphatic spread of ASP5354 after injection of the drug will also be assessed using a binary “Yes or No” question.
- The fluorescence intensity of the LN will be qualitatively assessed using a Likert Scale (0 = None; 1 = Mild; 2 = Moderate; and 3 = Strong).
- The radioactivity count will be collected for all the LNs identified by ASP5354 and/or SoC.
- The number of LN(s) with metastatic spread will be assessed based on histopathologic review.
Note: Histopathology review will be conducted per standard practice at each site.

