4.2 Scientific Rationale for Study Design

This is an open label dose finding study to determine the optimal dose for lymphatic mapping in participants undergoing lymphatic mapping and SLN biopsy with a radioisotope as part of SoC. Radioisotope is used routinely for lymphatic mapping in localized breast cancer (blue dye may also be used) and melanoma and provides a unique opportunity to investigate ASP5354 as a lymphatic mapping agent in participants already undergoing this procedure.

Based on the nonclinical data of fastest transit time and strength of fluorescence of 0.1 mg in minipigs, the starting dose is 0.2 mg was selected. This will decrease the possibility of starting with a dose that may not lead to visualization in human participants. Treatment will be staggered so the data in the first 3 participants treated can be analyzed to determine whether to dose above and below 0.2 mg or use 2 higher doses. Optimal dose determination will require an inferior dose and a comparable higher dose. Important characteristics of an

optimal dose will include fluorescence of lymphatic tissue based on histopathologic confirmation and intensity of fluorescence.

The current study design will allow sequential assessment for safety, tolerability and ability for a given dose to provide LN visualization before exposing additional subjects to ASP5354. LN identification is binomial (Yes or No), as such descriptive statistics will be used for analysis.

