ASP5354 will be injected subcutaneously at a minimum of 2, and up to 4. sites of equally divided subareolar injections. Please refrain from massaging the area of drug administration. After approximately 5 to 10 minutes, lymphatic mapping will then occur based on intraoperative fluorescence visualization using ASP5354. LNs will be identified by NIR-F imaging, followed by identification with the gamma probe. In the event that NIR-F imaging does not detect LN after approximately 15 minutes, the gamma probe should be used for LN identification. When the LN is detected with the gamma probe first, NIR-F imaging should be attempted again for LN visualization. Dissection of the LN will be conducted following identification by NIR-F imaging and/or the gamma probe. Before completing the surgery, NIR-F imaging and the gamma probe will be used to confirm further presence of other LNs, with further dissection and LN removal if indicated.

Melanoma

Arm/ IP Name	Melanoma 0.05 mg/ ASP5354	Melanoma 0.2 mg/ ASP5354	Melanoma 0.6 mg/ ASP5354
Use	test product	test product	test product
Dose	0.05 mg	0.2 mg	0.6 mg
Concentration	1.0 mg/mL	1.0 mg/mL	1.0 mg/mL
Volume	0.05 ml in total	0.2 ml in total	0.6 ml in total
Frequency	single dose	single dose	single dose
Route	intradermal injection	intradermal injection	intradermal injection
Location	peritumoral	peritumoral	peritumoral
Injection site	Minimum of 2, up to 4, sites equally divided injections	Minimum of 2, up to 4, sites equally divided injections	Minimum of 2, up to 4, sites equally divided injections
Duration	single dose	single dose	single dose

Arm/ IP Name	Melanoma 1 mg/ ASP5354	Melanoma 2 mg/ ASP5354
Use	test product	test product
Dose	1 mg	2 mg
Frequency	single dose	single dose
Concentration	1.0 mg/mL	1.0 mg/mL
Volume	1.0 mL in Total	2.0 mL in total
Frequency	single dose	single dose
Route	intradermal injection	intradermal injection
Location	peritumoral	peritumoral
Injection site	Minimum of 2, up to 4, sites equally divided injections	Minimum of 2, up to 4, sites equally divided injections
Duration	single dose	single dose

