7.1.1 Primary and Secondary Efficacy Assessments

Either during or post-operatively, the investigator will evaluate the details of all the LNs identified either by ASP5354 or Gamma Probe. These data will be captured to eCRF.

Following data is captured in eCRF per participant.

- Identification of at least 1 LN detected by ASP5354 and/or Tc-99mSC or Lymphoseek
- Times of injection of ASP5354 and Tc-99mSC or Lymphoseek
- Location (i.e., 3 and 9 o'clock) of ASP5354 administration
- Time of start of surgery
- Time of surgical identification of the LN(s) by ASP5354
- Time of incision for lymphatic mapping
- Time of removal of first LN
- Time of end of surgery
- Transdermal visualization of lymphatic spread of ASP5354 after injection

Following data is captured in eCRF per LN.

- “Sentinel LN” or “Non-sentinel LN”
- Method of identification (ASP5354 and/or Tc-99mSC or Lymphoseek)
- Dissection of LN tissue identified*
- Histopathologic confirmation of LN tissue by pathologist*

- Histopathologic confirmation of metastatic spread by pathologist*
- Likert scale:
The intensity of fluorescence will be qualitatively assessed during surgery by the investigator, by direct examination of the LN. Likert Scale (0 = None, 1 = Mild, 2 = Moderate and 3 = Strong) will be used to determine the intensity of fluorescence at the time point of the LN identification.
- Radioactivity count:
The radioactivity count of all the LNs identified by ASP5354 and /or Tc-99mSC or Lymphoseek will be counted with gamma probe.
* may not be collected in case of Non-Sentinel LN

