7.1.2 Signal Background Ratio

Video recording by NIR-F device is also required to evaluate the visualization of LN by ASP5354. Start recording a video at the time of injection of ASP5354 and continue until the first lymph node is visualized. For the remaining lymph nodes visualized, it is recommended to use video recording, but capturing images with the device is also acceptable. For further details, please refer to the Imaging Charter.

SBR is calculated by external reviewer based on the video recording by NIR-F device. Fluorescence images will be captured and recorded from injection time of ASP5354 until last LN is dissected. Images will be captured on a NIR-F and overlay view (if available) for all the LNs identified by ASP5354. SBR will be calculated as follows [Hoogstins et al, 2019]:

$$\text{SBR} = \frac{\text{mean region of interest}}{\text{mean signal background}}$$

Additional detail will be provided in the Imaging Charter.

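### The order of NIR-F and gamma-probe detection is not listed per node, so neither the ASP5354 rate nor the SoC rate can be read as independent detection

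*Protocol*

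**What the plan says.** - **Gamma probe first, then NIR-F.** NIR-F is used first. If no node appears after about 15 minutes (breast cancer) or 15 to 30 minutes (melanoma), the surgeon may turn to the gamma probe. Protocol Section 4.1, the synopsis and Table 1 footnote 15 then instruct: "When the LN is detected with the gamma probe first, radioactivity will be measured and then NIR-F imaging should be attempted again". Section 6.1.1 repeats it for both tumor types: "When the LN is detected with the gamma probe first, NIR-F imaging should be attempted again for LN visualization".
- **NIR-F first, then gamma probe.** The same paragraph of Section 4.1 has the probe tried on every node that ASP5354 shows, to measure radioactivity.
- **Data listed.** Section 7.1.1 lists, per node, "Method of identification (ASP5354 and/or Tc-99mSC or Lymphoseek". It lists, per participant, "Time of surgical identification of the LN(s) by ASP5354". No gamma detection time is listed. The Likert score "will be used to determine the intensity of fluorescence at the time point of the LN identification".
- **Counting.** SAP Section 4.4.1.1 counts nodes identified by ASP5354, by SoC, by either and by both. The percentages use one denominator, all histopathologically confirmed nodes (or sentinel nodes) identified intraoperatively (footnotes c and d). It has no rule for a node that is positive only on the second method's look. No estimand is defined.
- **Use.** The comparison with SoC is a secondary endpoint and one of the four listed inputs to the Visualization Review Committee (VRC) dose decision. The first branch turns on visualization in all three participants at 0.2 mg: "If < 3 participants at 0.2 mg dose level have LN visualization with histopathologic confirmation on VRC review", the next levels are 0.6 and 1 mg instead of 0.05 and 0.6 mg.

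**The concern.** A small difference between ASP5354 and SoC can arise in two ways. ASP5354 may have led the surgeon to the nodes, or the probe may have located them and they then fluoresced on a directed second look. These say different things about an agent meant for lymphatic mapping. The same holds in reverse: part of the SoC count may come from nodes whose position NIR-F had already shown. If order is not recorded for each node in theatre, it cannot be reliably rebuilt at analysis, and the planned SoC comparison cannot say which of these it measures.

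**Working it through.** The plan gives no detection rate by method and no repeat-look success rate. Its nearest figure, 3 levels x 12 = 36 participants per tumor type, reproduces but does not bear on this point. All rates and node counts below are assumptions.

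**1. Effect of one node.** Let N be the shared denominator, A the nodes credited to ASP5354 and S those credited to SoC. The difference is (A - S)/N.

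- A confirmed gamma-first node is already in N and S. Crediting its repeat look adds 1 to A: +1/N.
- A confirmed NIR-F-first node is already in N and A. Crediting its later probe reading adds 1 to S: -1/N.

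With 1, 2 or 3 confirmed nodes per participant, 1/N is 33.3, 16.7 or 11.1 points at 3 participants, and 8.3, 4.2 or 2.8 points at 12.

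**2. Two histories, one table.** Take N = 20.

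| | History A | History B |
|---|---|---|
| NIR-F first, then probe-positive | 14 | 10 |
| NIR-F only | 2 | 2 |
| Gamma first, NIR-F positive on repeat look | 0 | 4 |
| Gamma only | 4 | 4 |
| ASP5354 | 16 | 12 + 4 = 16 |
| SoC | 14 + 4 = 18 | 10 + 8 = 18 |
| Both | 14 | 10 + 4 = 14 |
| Either | 20 | 20 |

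The four SAP counts agree in every row, and the difference is (16 - 18)/20 = -10 points in both. Yet NIR-F led to 16 nodes in A and 12 in B.

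**3. How far the counting rule moves History B.**

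| Second looks credited | ASP5354 | SoC | Difference |
|---|---|---|---|
| Neither | 12/20 | 8/20 | +20 points |
| Probe readings only | 12/20 | 18/20 | -30 points |
| NIR-F repeat looks only | 16/20 | 8/20 | +40 points |
| Both | 16/20 | 18/20 | -10 points |

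If 2 rather than 4 of the 8 gamma-first nodes fluoresced, the last row would be (14 - 18)/20 = -20. Exact 95% intervals for ASP5354 are 36 to 81% at 12/20, 46 to 88% at 14/20 and 56 to 94% at 16/20. The +20 row is not an independent comparison either: NIR-F goes first by design, so the probe can be first only where NIR-F has not yet shown the node.

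**4. The 3/3 check at 0.2 mg.** Let p be the chance that a participant has a confirmed node seen by NIR-F before the probe, g the probe's success and r the repeat-look success. Treating the methods as independent, the any-look rate is p + (1 - p)gr, and P(3/3) is its cube. I set g = 0.90; Protocol Section 2.2 gives only a rate above 90% for radioisotope, blue dye or both in breast cancer.

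| p | r = 0 | r = 0.25 | r = 0.50 |
|---|---|---|---|
| 0.3 | 2.7% | 10% | 23% |
| 0.5 | 12.5% | 23% | 38% |
| 0.7 | 34% | 45% | 58% |

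For example, p = 0.5 and r = 0.5 give 0.5 + 0.5 x 0.9 x 0.5 = 0.725, and 0.725 cubed = 0.381.

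**The case against.** The strongest reply is that the text already settles the counting. The repeat look is made for visualization, the method item allows both, the SAP has a row for nodes found by both, and Section 4.2 says the important characteristics of an "optimal dose will include fluorescence of lymphatic tissue based on histopathologic confirmation and intensity of fluorescence". That stands: a gamma-first node that fluoresces would naturally be credited to both methods, and this is not an error. It does not help the reader of the tables to tell the two histories apart.

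Second, the primary decision compares doses with one another, no hypothesis is tested, and the VRC includes investigators who treated participants and sees individual listings. They may know which method came first. This makes the 3/3 consequence minor, as does the fact that both branches test 0.2 and 0.6 mg and levels can be added later. It does not carry the order into the final SoC comparison.

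Third, the recordings. From "Start recording a video at the time of injection of ASP5354 and continue until the first lymph node is visualized" a reader might infer that later nodes go unrecorded. The documents do not support that: Section 7.1.2 also requires images from injection until the last node is dissected, and Table 1 footnote 16 covers the entire surgery. The images may show when a node fluoresced. They do not show whether the probe had already located it, and no gamma time is listed to set beside them.

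Fourth, the VRC Charter, the Imaging Charter and the eCRF guideline were not available and may hold a rule. If so, Section 7.1.1 and the SAP should match it.

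**Conclusion.** The point holds as a cheap improvement. Under SAP footnotes c and d, each second-look node that is counted moves the difference by exactly 1/N, up for a gamma-first node and down for an NIR-F-first node. That step is arithmetic. How many such nodes there will be is unknown, and every worked size above rests on assumed rates.

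A reader might infer that the repeat look tilts the comparison toward ASP5354. The documents do not support a net direction, because the probe is likewise used on nodes NIR-F has already shown. Nor do they support the inference that contrasts between doses are biased in a known direction; that would depend on how repeat-look success varies with dose, which is not given. The 3/3 check is affected only when a participant's sole confirmed visualized node came from a repeat look. For a gamma-first node it is also unclear which look the Likert score refers to.

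**What to change.** - In Protocol Section 7.1.1, add one symmetric per-node eCRF item for order of detection: NIR-F first, then probe-positive; gamma first, then NIR-F positive on repeat look; NIR-F only; gamma only; found after another agent. State which look the Likert score refers to.
- In SAP Section 4.4.1 and the VRC listings, show ASP5354 results both before gamma localisation and including repeat-look positives. Tabulate nodes by first method, and state that the SoC rate is not independent either, because NIR-F-first nodes are probed with their position known.
- State which version is read at the 0.2 mg review. The default reading of the current text is any look.

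The cost is one field and a few table and listing rows. The pre-gamma rate will be lower, because it scores slow-transit nodes as not detected, and it depends on when the surgeon turns to the probe. That is why both versions are shown and neither replaces the other. Surgical procedure, doses and the dose rule do not change.

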4.2 Scientific Rationale for Study Design

This is an open label dose finding study to determine the optimal dose for lymphatic mapping in participants undergoing lymphatic mapping and SLN biopsy with a radioisotope as part of SoC. Radioisotope is used routinely for lymphatic mapping in localized breast cancer (blue dye may also be used) and melanoma and provides a unique opportunity to investigate ASP5354 as a lymphatic mapping agent in participants already undergoing this procedure.

Based on the nonclinical data of fastest transit time and strength of fluorescence of 0.1 mg in minipigs, the starting dose is 0.2 mg was selected. This will decrease the possibility of starting with a dose that may not lead to visualization in human participants. Treatment will be staggered so the data in the first 3 participants treated can be analyzed to determine whether to dose above and below 0.2 mg or use 2 higher doses. Optimal dose determination will require an inferior dose and a comparable higher dose. Important characteristics of an

optimal dose will include fluorescence of lymphatic tissue based on histopathologic confirmation and intensity of fluorescence.

The current study design will allow sequential assessment for safety, tolerability and ability for a given dose to provide LN visualization before exposing additional subjects to ASP5354. LN identification is binomial (Yes or No), as such descriptive statistics will be used for analysis.

4.3 Dose Rationale

The starting dose is 0.2 mg (0.2 mL of a 1 mg/mL ASP5354 solution) per participant, which will be locally administered as subcutaneous (breast cancer) or intradermal (melanoma) injection. The rationale for the starting dose is based on the results of the toxicology studies in rabbits and the phase 1 study after intravenous administration (Study 5354-CL-0001) and the estimated clinical efficacious dose in humans. ASP5354 solution at up to 5 mg/mL showed no local irritation after subcutaneous and intramuscular injection in rabbits (Studies 5354-TX-0101 and 5354-TX-0102), indicating 1 mg/mL ASP5354 solution can be used in this study. ASP5354 is confirmed safe and well tolerated up to 24 mg after intravenous administration in the phase 1 study (Study 5354-CL-0001). So, the starting dose of 0.2 mg is considered to be safe. The estimated clinical efficacious dose of 0.2 mg (0.2 mL of a 1 mg/mL ASP5354 solution) per participant is proposed because 0.1 mL of a 1 mg/mL ASP5354 solution provided comparable LN visualization after injection as compared with 0.1 mL of a 2.5 or 5 mg/mL ICG solution in the nonclinical study in Göttingen minipigs (Study 5354-PH-0004).

The potential highest dose tested in this study will be 4 mg (4 mL of a 1 mg/mL ASP5354 solution) per participant, which is well below the highest intravenous dose of 24 mg tested in the phase 1 study (Study 5354-CL-0001).

4.4 End of Study Definition

The study start is defined as the date the first participant signs informed consent. The end of the study is defined as the last visit or scheduled procedure shown in the Schedule of Assessments for the last participant in the study.

5 STUDY POPULATION

All screening assessments must be completed and reviewed to confirm the potential participant meets all eligibility criteria. Prospective approval of protocol deviations to eligibility criteria (also known as protocol waivers or exemptions) is not permitted.

5.1 Inclusion Criteria

Participant is eligible for participation in the study if all of the following apply:

1. Institutional Review Board (IRB)/Independent Ethics Committee (IEC) approved written informed consent and privacy language as per national regulations (e.g., Health Insurance Portability and Accountability Act authorization for US study sites) must be

obtained from the participant prior to any study-related procedures (including withdrawal of prohibited medication, if applicable).

2. Participant has been diagnosed with localized breast cancer (female only, stage 0 to 2, N0 and M0) or melanoma (stage 1 to 2, N0 and M0) and is scheduled to undergo surgical intervention for SLN detection and removal using Tc-99mSC or Lymphoseek as part of SoC.
3. Participant is considered an adult (≥ 18 years of age) according to local regulation at the time of signing the informed consent form (ICF).
4. Female participant is not pregnant (see [Section 10.2 Appendix 2 Contraception Requirements]) and at least 1 of the following conditions apply:
 - a. Not a woman of childbearing potential (WOCBP) (see [Section 10.2 Appendix 2 Contraception Requirements])
 - b. WOCBP who agrees to follow the contraceptive guidance (see [Section 10.2 Appendix 2 Contraception Requirements]) from the time of informed consent through at least 30 days after final study treatment administration.
5. Female participant must agree not to breastfeed starting at screening and throughout the study period and for 30 days after final study treatment administration.
6. Female participant must not donate ova starting at first dose of IP and throughout the study period and for 30 days after final study treatment administration.
7. Male participant with female partner(s) of childbearing potential (including breastfeeding partner) must agree to use contraception (see [Section 10.2 Appendix 2 Contraception Requirements]) throughout the treatment period and for 30 days after final study treatment administration.
8. Male participant must not donate sperm during the treatment period and for 30 days after final study treatment administration.
9. Male participant with pregnant partner(s) must agree to remain abstinent or use a condom for the duration of the pregnancy throughout the study period and for 30 days after final study treatment administration.
10. Participant agrees not to participate in another interventional study while participating in the present study.

Waivers to the inclusion criteria will **NOT** be allowed.

